## 2.0 Specific Aims and Hypothesis

The **first primary aim** is to demonstrate how targeting the precuneus with rTMS impacts functional activation (FA) in individuals with schizophrenia during EM tasks. We predict that, compared to sham stimulation, 1 Hz rTMS will result in decreased FA of the precuneus and 20 Hz rTMS will result in increased FA of the precuneus. The **second primary aim** is to demonstrate how targeting the precuneus with rTMS impacts precuneus functional connectivity (FC) in individuals with schizophrenia. We predict that compared to sham stimulation, FC between the precuneus, the DLPFC, the hippocampus, and the ACC will be decreased in response to 1 Hz rTMS and increased in response to 20 Hz rTMS. The **third primary aim** is to characterize the relationships between EM performance and changes in precuneus functional activation and connectivity. We predict that improved EM performance will be associated with increased precuneus functional activation and connectivity, while poorer EM performance will be associated with decreased precuneus functional activation and connectivity. The **secondary aim** is to characterize how targeting the precuneus with rTMS affects episodic memory performance in individuals with schizophrenia. We predict that compared to sham stimulation, 1 Hz rTMS will impair EM performance and that 20 Hz rTMS will improve EM performance.

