### 3.0 Study Design

This will be a single site pilot study. 30 subjects with EPP, defined as medical record documentation of the onset of clinically significant psychotic symptoms within the past ten years, will be enrolled. Prior to randomization (Session 1), subjects will undergo fMRI during EM and RS paradigms. This baseline scan will also include a high-resolution structural sequence for neuronavigation purposes. Then on three separate days each occurring one-week apart, subjects will receive one session of inhibitory (1 Hz) rTMS, one session of excitatory (20 Hz) rTMS, and one sham stimulation session targeting the precuneus. The order of the three interventions will be randomized. Immediately following each rTMS or sham session, subjects will undergo repeat fMRI during EM and RS paradigms. We will also examine the effect of rTMS on EM performance.

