### *Sample Size*

We plan to enroll 30 subjects and anticipate a 20% drop out rate, yielding 24 completers. This is consistent with our previous clinical trial efforts, including a study of adjunct rTMS for cognitive impairment. For all planned analyses, a total of 24 subjects in a cross-over design will result in 0.8 power to detect an assumed treatment difference at medium effect size 0.6; using an alpha level of 0.05 and conservatively assumed a within-subject correlation of 0.5. As no precuneus rTMS pilot data was available, this standardized effect size of 0.6 is considered a conservative estimate to detect significant results.

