#### *Statistical Analyses*

[figure not shown]
Intent-to-treat (ITT) analysis will be conducted, and thus all randomized subjects will be included. ITT is the most conservative approach for detecting a treatment effect, because the inclusion of subjects who do not complete the intervention will serve to underestimate rather than overestimate any treatment effect. Sensitivity analyses including a subset analysis using a “completers only” analysis will be performed to test the robustness of the findings. Statistical tests will be performed based on two-sided test at the 5% level of significance.

Descriptive characteristics at baseline will be summarized for the whole sample. For continuous variables, the mean and standard deviation will be presented. For categorical variables, the number and percent will be reported.

Primary analyses: For each subject, change scores in activation of the precuneus (aim 1), functional connectivity (aim 2), and EM performance (aim 3) will be calculated at each treatment by using (post - baseline). We will employ a mixed model for repeated measures ANCOVA, of the general form for each measure:  $change_{ijk} = \mu + \alpha_i + b_{ij} + \gamma_k + \beta X_{ijk} + \tau_d(i, k) + e_{ijk}$ , where  $\mu$  is overall mean;  $\alpha_i$  is the effect of the  $i$ th treatment sequence ( $i = 1, 2, \dots, 6$ );  $b_{ij}$  is the random effect with variance  $\sigma_b^2$  for the  $j$ th subject ( $j = 1, 2, \dots, 24$ ) of the  $i$ th treatment sequence;  $\gamma_k$  is the period effect ( $k = 1, 2, 3$ );  $\beta X$  is the baseline value;  $\tau_d(i, k)$  is the direct effect of the treatment administered in period  $k$  of sequence group  $i$ ; and  $e_{ijk}$  is the random error with variance  $\sigma^2$  for the subject in period  $k$ . Based on this model, we will compare the treatment difference in change score between 1 Hz and Sham as well as 20 Hz and Sham. Under the assumption of missing at random, this mixed effect model will provide the unbiased estimates.

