Secondary analyses: We expect two mediation relations: (1) the treatment affects the connectivity through the activation of the precuneus; and (2) the treatment affects the EM performance through the activation of the precuneus. We use the first mediation as an example. The following 3 equations proposed by Baron and Kenny will be analyzed in order to establish mediation:  $change_{ijk} = \mu + \alpha_i + b_{ij} + \gamma_k + \beta X_{ijk} + \tau_d(i, k) + e_{ijk}$  (1);  $change_{ijk} = \mu + \alpha_i + b_{ij} + \gamma_k + \beta X_{ijk} + \gamma M_{ijk} + \tau_d(i, k) + e_{ijk}$  (2); and  $M_{ijk} = \mu + \alpha_i + b_{ij} + \gamma_k + \beta X_{ijk} + \tau_d(i, k) + e_{ijk}$  (3). Four steps are to be evaluated. First, a significant relation of treatment to the change in connectivity is required in (1). Second, a significant relation of treatment to the change in activation of the precuneus is required in (3). Third, mediator, the change in the activation of the precuneus, must be significantly associated with change in connectivity when both treatment and mediator are controlled as covariates. Fourth, the coefficients of treatment in (1) must be larger (in absolute value) than the coefficients of treatments in (2). If four steps are met, we will consider that the change in activation of the precuneus is mediator of the relationship between treatment and change in connectivity.

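### The primary model labelled aim 3 tests the rTMS effect on episodic memory, not the association that is the third primary aim; the memory–activation link sits only in a secondary mediation analysis and the memory–connectivity link has no model

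*Combined protocol and SAP*

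**What the plan says.** Section 2.0 sets three primary aims and one secondary aim. The third primary aim "is to characterize the relationships between EM performance and changes in precuneus functional activation and connectivity", and it carries a direction: "We predict that improved EM performance will be associated with increased precuneus functional activation and connectivity". The secondary aim "is to characterize how targeting the precuneus with rTMS affects episodic memory performance in individuals with schizophrenia". Section 3.0 introduces that effect as an addition: "We will also examine the effect of rTMS on EM performance".

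The closing paragraph of section 1.0 numbers things differently. It lists three effects of rTMS to be studied: precuneus activation, connectivity, and performance on the in-scanner EM task. The association between them is not on that list.

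Section 13.0, Primary analyses, states that "change scores in activation of the precuneus (aim 1), functional connectivity (aim 2), and EM performance (aim 3) will be calculated at each treatment". One model is given for each measure, with sequence, random subject, period, baseline and treatment terms. Its stated inference is: "we will compare the treatment difference in change score between 1 Hz and Sham as well as 20 Hz and Sham".

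Secondary analyses name two mediation relations. The first runs from treatment to connectivity through activation and is written out as equations (1) to (3). The second is that "the treatment affects the EM performance through the activation of the precuneus"; its equations are left to analogy. Brain Imaging Analyses cover Aims 1 and 2 only.

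Sample Size (section 3.0) and Power Analyses (section 13.0) make the same claim: "For all planned analyses, a total of 24 subjects in a cross-over design will result in 0.8 power to detect an assumed treatment difference".

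**The concern.** An analyst who follows section 13.0 will report treatment contrasts on EM under the aim 3 label. Those contrasts answer what section 2.0 calls the secondary aim. The directional prediction of the third primary aim then has no primary test for activation and no model at all for connectivity.

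Someone will have to write the missing model later, and must then decide whether treatment is in it, whether the slope is within or between subjects, and which EM score is used. Different choices estimate different quantities. If they are made after the data are seen, they can decide whether the prediction appears confirmed. The power statement gives no help, because it is framed for a treatment difference.

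**Working it through.** **1. Questions against models.**

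| Question | Standing in section 2.0 | Model in section 13.0 |
|---|---|---|
| rTMS effect on activation | First primary aim | Primary analyses; Brain Imaging, Aim 1 |
| rTMS effect on connectivity | Second primary aim | Primary analyses; Brain Imaging, Aim 2 |
| EM with activation | Third primary aim | Only equation (2) of mediation relation (2), by analogy; secondary |
| EM with connectivity | Third primary aim | None: connectivity is only ever an outcome and is never related to EM |
| rTMS effect on EM | Secondary aim | Primary analyses, labelled aim 3 |

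The mediation route does not replace a direct test. Its only stated conclusion is mediation, and its steps require significant treatment effects on both outcome and mediator. The third aim sets no such condition.

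**2. The plan's power figure.** Inputs from Power Analyses and Statistical Analyses: 24 completers, effect 0.6, within-subject correlation 0.5, two-sided 0.05. Standardized paired difference = 0.6/√(2 × (1 − 0.5)) = 0.6. A two-sided paired t-test with n = 24 (23 df) has power 0.804, which reproduces 0.8. Enrolment also agrees: 24/(1 − 0.20) = 30. The figure is therefore a treatment-difference calculation.

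**3. Degrees of freedom for a within-subject slope.** 24 subjects × 3 periods = 72 values. Sequence and baseline are constant within subject and cost nothing here.
- With treatment: 72 − 24 (subjects) − 2 (period) − 2 (treatment) − 1 (slope) = 43.
- Without treatment: 72 − 24 − 2 − 1 = 45.

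**4. Detectable correlation.** Fisher z, 80% power, two-sided 0.05: 1.960 + 0.842 = 2.802.
- Within subject, without treatment: tanh(2.802/√44) = 0.40.
- Within subject, with treatment: tanh(2.802/√42) = 0.41.
- One value per subject: tanh(2.802/√21) = 0.55.
- With treatment, 20 completers (35 df): 0.45; 30 completers (55 df): 0.36.
- If four tests are assumed and Bonferroni is applied (alpha 0.0125), 24 completers: 0.47 within subject with treatment, 0.62 with one value per subject.

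A simulation of the plan's random-subject model, with treatment and the split predictor, gave power 0.812 at a correlation of 0.407, so the approximation is adequate.

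**5. Why the treatment term must be stated.** Assume, for illustration, that rTMS shifts both activation and EM by −0.6, 0 and +0.6 SD, and that they share nothing else. With SD 1 and within-subject correlation 0.5, the within-subject residual variance is 0.5.
- Treatment sum of squares and cross-product: 24 × (0.36 + 0 + 0.36) = 17.28.
- Residual sum of squares after subjects and period: (48 − 2) × 0.5 = 23.
- Correlation without treatment in the model: 17.28/(17.28 + 23) = 0.43. With treatment: 0.
- At ±0.3 SD: 24 × 0.18 = 4.32, and 4.32/(4.32 + 23) = 0.16. With treatment: 0.

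Simulated means agree (0.430 and 0.156 without treatment, 0.00 with it).

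**The case against.** The strongest defence is that the label follows section 1.0, where EM task performance is the third effect listed, in the same order as Primary analyses. This is plausible and should be granted. It means that sections 1.0, 2.0 and 13.0 disagree on the standing of the EM treatment contrasts, not that section 13.0 alone is wrong. It does not supply a model for the association that section 2.0 calls primary. Nor does reading the label as a mere tag for the variable, since no other primary model is given.

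A reader might infer that the third aim has no analysis at all. The documents do not support that. Equation (2) of the second mediation relation would yield a treatment-adjusted EM-on-activation coefficient, so that half is misplaced. Only the connectivity half is absent.

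A reader might also infer that treatment must be in the model, and that the 0.43 in the illustration is spurious. It is a real association induced by stimulation. Section 2.0 predicts that 20 Hz raises activation, connectivity and EM and that 1 Hz lowers them, so the aim can be read to include it. The plan's mediation equation does not settle the matter, because it serves another purpose.

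On power, the sentence does say that it concerns a treatment difference; only its reach to every planned analysis is too wide.

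Finally, this is a single-site pilot and the aim's verb is to characterize. That lowers the stakes, but the protocol itself makes the aim primary and predicts its direction. Some figures are not visible to check, but the running text points to no further analysis.

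**Conclusion.** The point holds in this form: one of three primary aims is not matched by a primary analysis, and the model carrying its label answers the aim that section 2.0 ranks as secondary. EM–activation is placed in a lower tier under a mediation conclusion; EM–connectivity has no model. The treatment contrasts for aims 1 and 2 are untouched.

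The stated 0.8 is arithmetically right for a treatment difference and says nothing about an association. The detectable correlations of about 0.40, 0.41 and 0.55 assume 24 completers with complete data and a single test at two-sided 0.05. The documents give no target association to compare them with.

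A count of four tests (activation plus three connections) is tempting but not established. Section 2.0 names the DLPFC, hippocampus and ACC, whereas Brain Imaging Analyses list the ACC and bilateral middle frontal gyrus, with regions defined on each side and no hippocampal region. The multiplicity figures are therefore examples only.

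**What to change.** 1. Reconcile sections 1.0, 2.0 and 13.0 so that the 1 Hz and 20 Hz contrasts against sham on EM change carry the label of the aim they answer. Under section 2.0 that is the secondary aim.
2. Add an Aim 3 model to Primary analyses: EM change on activation change, and separately on change in each connectivity measure analysed for Aim 2, keeping the sequence, period, baseline and random-subject terms. If the within-subject slope is the target, split the predictor into subject mean and within-subject deviation.
3. State before data are seen which version is primary: without treatment (the association including what stimulation induces) or with treatment (the association beyond the treatment effect). Report the other as a sensitivity analysis. Give slopes with 95% confidence intervals.
4. Name the EM score, since the task in section 6.0 records both accuracy and reaction time. Count the tests from the regions actually analysed, and resolve the hippocampus discrepancy.
5. In Sample Size and Power Analyses, limit the 0.8 to treatment differences and give the detectable correlation for Aim 3: about 0.40 within subject without treatment, 0.41 with it, or 0.55 with one value per subject.

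The cost is wording and a few extra fits on data the design already collects; no visit or scan changes. The drawback is additional tests. Any multiplicity correction raises the detectable correlation, for example from 0.41 to about 0.47 within subject with treatment if four tests are assumed.

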**Brain Imaging Analyses:** **Aim 1.** Data analysis of the blood-oxygen level-dependent (BOLD) time series will utilize standard preprocessing through the AFNI software package. Standard preprocessing includes motion correction, despiking, detrending, smoothing, and exclusion of signal and motion outlier time points. Each condition's timing will be convolved with a hemodynamic response function to model an ideal response for that condition. General linear modeling will provide a regression coefficient estimate (beta) of the BOLD response to each condition (Target correct; Foil correct; Target incorrect; Foil incorrect). We will also include regressors of no interest for motion and motion derivatives to reduce noise. For our primary analysis, we will create a region of interest (ROI) as a 10-mm radius sphere around our rTMS target in the precuneus. **fMRI Contrast:** Each event type will be modeled separately. Brain activity will be examined by contrasting the estimated beta coefficients for correct trials only (Target correct vs. Foil correct). We will **extract the mean response from this contrast from our precuneus ROI** and evaluate the aim via a mixed model for repeated measures. **Aim 2.** Beyond standard preprocessing, time-series data will be filtered to extract low frequency (< 0.08 hz) BOLD data. The ANATICOR approach (within AFNI) will be used to reduce noise from physiological or hardware sources. ANATICOR utilizes tissue segmentation to control for spatially coherent fluctuations emanating from non-gray matter. Structural regions of interest (ROIs) will be defined on each side with Talairach-based atlases available via AFNI software for the ACC and bilateral middle frontal gyrus, in addition to the spherical precuneus ROI. Visual inspection of ROIs will ensure their correct position. The mean preprocessed time series will be extracted from each ROI, and time-series correlations between ROIs will be calculated. These correlations will be used as the dependent variable in a mixed model for repeated measures ANCOVA, with post-hoc tests as necessary. Supplementary analyses will examine connectivity differences of the precuneus ROI across the entire brain (corrected  $p < .05$ ).

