## ATTACHMENT 1: Study Procedures Table

Visit Number	1 c	2	3	4	5 d
Day b		0	7	14	28
Informed Consent	X				
Screening (Demographics, Inc/Exc, Medical & Psychiatric History of Self and Family)	X				
SCID V a	X				
Physical Exam	X				
CGI-S	X	X	X	X	
CGI-I		X	X	X	
Vitals	X	X	X	X	
Urine Drug Screen	X				
Pregnancy Test	X	X	X	X	
Motor Threshold Determination	X				
MRI – Baseline & Baseline EM Task	X				
Randomization (Order of Study Intervention)		X			
Neuro Navigation		X	X	X	
rTMS/sham Administration		X	X	X	
Post Stimulation MRI-EM Task		X	X	X	
PANSS	X				
AIMS	X	X	X	X	
C-SSRS	X	X	X	X	
Adverse Events	X	X	X	X	X
Concomitant Medication	X	X	X	X	X
a If subject received a SCID interview within 6 months of screening, it may not be repeated at the discretion of the PI					
b Ideal time frame for administration will be on each Monday of three consecutive weeks. A total of 3 sessions. Visit window deviations will be granted at the discretion of the PI and will not be a protocol violation.					
c Visit window for Visit 1 is 0-30 days					
d Visit 5 may occur by phone and ideally will occur 14 days after Visit 4. Visit window deviations will be granted at the discretion of the PI and will not be a protocol violation.					

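### The single Visit 1 baseline is both subtracted and used as a covariate: the subtraction gains nothing, and a subject with an unusable baseline loses valid post-session data for that outcome

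*Combined protocol and SAP*

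**What the plan says.** - **Outcome.** Section 13.0, Statistical Analyses, lists under the primary analyses "change scores in activation of the precuneus (aim 1), functional connectivity (aim 2), and EM performance (aim 3"), and these "will be calculated at each treatment by using (post - baseline").
- **Covariate.** The model also contains a term βX, where βX "is the baseline value".
- **Contrasts.** From this model "we will compare the treatment difference in change score between 1 Hz and Sham as well as 20 Hz and Sham".
- **One baseline.** Section 3.0 says "Prior to randomization (Session 1), subjects will undergo fMRI during EM and RS paradigms". The Attachment 1 row "MRI – Baseline & Baseline EM Task" is marked at Visit 1 only. Visits 2 to 4 have a post-stimulation scan and no pre-stimulation scan.
- **Analysis set.** Under intent-to-treat, "all randomized subjects will be included". Missing at random is invoked, but no rule covers a missing or unusable baseline.
- **Aim 2, second description.** Under Brain Imaging Analyses in the same section, the ROI correlations are the outcome, with no mention of change: "These correlations will be used as the dependent variable in a mixed model for repeated measures ANCOVA".
- **Safeguards.** Section 6.0 has images checked during scanning, Section 11.0 allows screening assessments to be repeated, and exclusion criterion 9 removes people who cannot tolerate MRI.

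**The concern.** In a crossover, each subject's treatments are compared with that subject's own sham session. A number that is constant within the subject carries no information about that comparison. Here the same Visit 1 value is subtracted in all three periods and then entered again as X.

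The subtraction can nevertheless do harm. A mixed model copes with a missing response in one period. It does not cope with an outcome that is undefined in every period, or with a missing covariate. If motion, artefact or task failure spoils the Visit 1 measure, all of that subject's post-session values for that measure fall out, although they identify both contrasts without it. The 20% allowance in the sample size is described as drop-out only, so it holds no reserve for this.

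**Working it through.** **1. The plan's own power figure.** Inputs from Section 13.0, Power Analyses: 24 completers, effect size 0.6, within-subject correlation 0.5, alpha 0.05; two-sided per Statistical Analyses.
- Standardized paired difference: 0.6 / √(2 × (1 − 0.5)) = 0.6.
- Noncentrality: 0.6 × √24 = 2.94. With 23 degrees of freedom, power is 0.804, which reproduces the stated 0.8. With the crossover residual degrees of freedom (44) it is 0.820.
- Enrolment: 30 × 0.8 = 24.

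**2. Subjects with all three sessions.** (post_active − base) − (post_sham − base) = post_active − post_sham, so the baseline cancels exactly. As a check, the planned model was fitted to one simulated crossover of 24 subjects in six sequences, with change or post-session value as outcome, each with and without X. All four fits gave treatment estimates of −0.8329 and 0.6781 and a standard error of 0.1902.

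**3. Subtraction when X is in the model.** Since change = post − X, a model for change with coefficient β is the model for post with coefficient β + 1. The fits show this: −0.167 for change and 0.833 for post. It is a relabelling and holds whichever sessions are missing.

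**4. Value of X under dropout.** Assumptions: 30 randomized, 6 dropouts, total variance 1, within-subject correlation 0.5, and a baseline as reliable as a post-session scan. Standard error of the 1 Hz–sham contrast:

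| Dropout pattern | With X | Without X | With X, 1 completer lost | With X, 3 completers lost |
|---|---|---|---|---|
| 6 after period 1 | 0.1993 | 0.2006 | 0.2036 | 0.2128 |
| 6 after period 2 | 0.1910 | 0.1915 | 0.1947 | 0.2026 |
| 3 after each | 0.1976 | 0.1985 | 0.2016 | 0.2105 |

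- Leaving X out costs 0.3% (0.1915/0.1910) to 0.7% (0.2006/0.1993).
- Losing one completer to a bad baseline costs about 2% (0.2016/0.1976 = 1.020).
- Losing three costs 6% to 7% (0.2105/0.1976 = 1.065).

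So even one lost completer costs more than X is worth.

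**5. Power if baselines are unusable.** The documents give no rate; 1 to 4 of 24 is an assumed range. Using the paired t that reproduces the plan's figure:

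| Completers with usable baseline | Power at 0.6 |
|---|---|
| 24 | 0.804 |
| 23 | 0.785 |
| 22 | 0.765 |
| 21 | 0.744 |
| 20 | 0.721 |

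**6. Baseline as a further response record.** In simulated complete crossovers (a few fits gave convergence warnings) the treatment estimates were unchanged, but the standard error depended on the variance assumption. If the baseline shares the post-session residual variance, the ratio to the planned standard error ran from 0.90 to 1.16 with equal noise. It rose by about 14% to 16% on average with baseline residual SD 1.5 times the post-session SD, and fell by about 7% with 0.6 times. Giving the baseline its own variance and covariance restored the planned standard error.

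**The case against.** The strongest reply is that the loss may never happen. The baseline precedes randomization, tasks are practised at Visit 1, images are checked during scanning, screening assessments may be repeated, and people who cannot tolerate MRI are excluded. The loss is also specific to an outcome: a failed memory-task run need not remove the resting-state measure. All of this stands, and it makes the point a risk. The safeguards are still partial. Outlier time points are removed in preprocessing, the Aim 1 contrast needs correct target and correct foil trials, and no eligibility criterion requires a usable functional baseline.

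A second reply is that the power loss is modest. One or two lost subjects leave 0.785 or 0.765, and the calculation ignores partial data from dropouts, which the mixed model keeps. This also stands.

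A reader might infer that the baseline adds nothing and cancels from every contrast. The documents do not support that. The planned set includes dropouts, who contribute some between-subject information, and X then helps slightly. The mediation models use a change score as mediator, so the cancellation in the two treatment contrasts does not carry over to them. Nor does the point argue for dropping the Visit 1 scan: Section 3.0 needs its structural image for neuronavigation.

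**Conclusion.** The point holds as a limited one. The subtraction is redundant in both primary contrasts: exactly so for subjects with all three sessions, and also under dropout once X is in the model. X itself is worth under 1% in standard error under the assumed variances. In return, the stated outcome rule discards valid post-session scans whenever the Visit 1 measure is unusable, which conflicts with the intent-to-treat statement.

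Its size depends on a rate the documents do not give. With an assumed 1 to 4 of 24 affected, power falls from 0.804 to between 0.785 and 0.721, on the plan's basis of exactly 24 completers. It would be wrong to conclude that the trial will lose these subjects or that the sample size was miscalculated; the stated 0.8 reproduces.

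**What to change.** In Section 13.0, Statistical Analyses, make the post-session value the response. Then choose one of two ways to keep the baseline:

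- **Joint model.** Enter the Visit 1 value as a further response record, with its own residual variance and its own covariance with the post-session values. Do not let it share the post-session residual variance, because that changes the standard error. Subjects without a usable baseline stay in, and subjects with missing sessions still borrow from theirs.
- **Simpler option.** Keep the baseline as covariate, state the rule for a missing or unusable baseline, and add a post-only analysis that keeps every subject with post-session data.

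Change from baseline can still be reported descriptively. Three other places need aligning: the mediation equations, which are written in change scores; the Aim 2 text under Brain Imaging Analyses, which uses the correlations themselves; and Section 2.0, which makes the treatment effect on memory performance a secondary aim while Section 13.0 lists it under the primary analyses.

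The cost is SAP wording and slightly more modelling, with no new data or visits. With complete data the treatment estimates are unchanged, and the standard error is essentially unchanged when the baseline has its own variance and covariance.

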## **13.0 Statistical Considerations**

### **Analyses**

#### *Power Analyses*

In terms of the power to detect a significant effect of precuneus directed rTMS on EM performance or neurocircuitry, there are no known calculations with EPP patients. We plan to enroll 30 subjects and anticipate a 20% drop out rate, thus yielding 24 completers. This is consistent with our previous clinical trial efforts in early phase psychosis populations, including a study of adjunct rTMS for cognitive impairment and negative symptoms. For all planned analyses, a total of 24 subjects in a cross-over design will result in 0.8 power to detect an assumed treatment difference at medium effect size 0.6; using an alpha level of 0.05 and conservatively assumed a within-subject correlation of 0.5. As no previous precuneus rTMS pilot study was available, this standardized effect size of 0.6 is considered to a conservative estimate to detect the significant results.

[figure not shown]

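### The four-step mediation rule requires a significant total effect and plans no interval for the indirect effect, and its single mediator slope mixes within- and between-subject association

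*Combined protocol and SAP*

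**What the plan says.** The secondary-analyses paragraph of section 13.0 (Statistical Analyses) expects precuneus activation to mediate the treatment effect on connectivity and on episodic memory (EM) performance. The first relation is worked as the example. Equation (1) regresses the change in outcome on treatment, equation (2) adds the mediator M, and equation (3) regresses M on treatment. All three carry sequence, period, baseline and a random subject effect. Change scores "will be calculated at each treatment by using (post - baseline").

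- Step 1: "First, a significant relation of treatment to the change in connectivity is required in (1").
- Step 2 asks the same of activation in equation (3).
- Step 3: the mediator "must be significantly associated with change in connectivity when both treatment and mediator are controlled as covariates".
- Step 4: "the coefficients of treatment in (1) must be larger (in absolute value) than the coefficients of treatments in (2").
- Decision: "If four steps are met, we will consider that the change in activation of the precuneus is mediator".

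For the primary model, the plan says "we will compare the treatment difference in change score between 1 Hz and Sham as well as 20 Hz and Sham". The mediation paragraph does not say whether steps 1 and 2 use those contrasts or an overall 2-df treatment test. Section 13.0 gives no standard error, interval or test for the indirect effect. Power Analyses claims, for 24 completers, "0.8 power to detect an assumed treatment difference at medium effect size 0.6", at alpha 0.05 and a within-subject correlation of 0.5.

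**The concern.** There are two separate weaknesses.

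**The gate and the missing interval.** The indirect effect is a × b, where a is the treatment effect on M and b is the slope of the outcome on M. If all of the effect runs through M, the total effect is a × b, which is smaller than a whenever b is below 1. Step 1 then tests a quantity smaller than the one the trial was sized for. A verdict without an interval also does not show how large an indirect effect the data allow, and the Background presents this pilot as a source of preliminary target-engagement data for later trials.

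**The blended slope.** Every subject receives all three conditions, so a is a within-subject quantity and the matching b is the within-subject slope. With M undivided and a random intercept, the fitted slope is a weighted mix of the within- and between-subject slopes. If subjects with larger average changes in activation also have larger average changes in the outcome, step 3 can be met with no within-subject link.

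**Working it through.** **Inputs from the plan:** 24 completers, difference 0.6, two-sided alpha 0.05, within-subject correlation 0.5, three periods, six sequences. **Assumed:** a = +0.6 for 20 Hz and −0.6 for 1 Hz; M and outcome each with total variance 1 and ICC 0.5; b = 0.4, 0.6 or 0.8; complete data, four subjects per sequence. Outcome variance does not grow with b.

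**1. The plan's own figure.** SD of a paired difference = √(2 × (1 − 0.5)) = 1. SE = √(2 × 0.5/24) = 0.204. Noncentrality = 0.6/0.204 = 2.94. Power is 0.804 on 23 df and 0.820 on 44 df, so the stated 0.8 reproduces for one contrast at a true difference of 0.6.

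**2. What step 4 measures.** The treatment coefficient in (2) is c − γa, where c is the coefficient in (1) and γ the slope on M. The step 4 difference is therefore γa, a point estimate of the indirect effect, used only as a larger/smaller check.

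**3. Cost of the gate (20 Hz against sham, per contrast).** Under full mediation the total effect is 0.6 × b. Step 1 power is by noncentral t on 44 df. The other rows are simulated with the planned models fitted by REML. The interval is a 95% Monte Carlo interval on a × within-subject b.

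| | b = 0.4 | b = 0.6 | b = 0.8 |
|---|---|---|---|
| Full mediation: total effect | 0.24 | 0.36 | 0.48 |
| Step 1 alone passes | 21% | 41% | 63% |
| Four-step rule | 18% | 39% | 61% |
| Interval | 66% | 83% | 83% |
| Total effect 0.6: four-step rule | 63% | 72% | 75% |
| Total effect 0.6: interval | 65% | 83% | 84% |

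Read as 2-df tests, the rule gives 30/65/89% under full mediation and 89/98/98% at total effect 0.6. Intervals at 97.5% on either contrast give 68/96/97%. These are not like for like, but on that reading nothing is lost at 0.6.

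**4. False claims from blending (within-subject link zero).** At ICC 0.5, step 3 is falsely significant in 9/16/29% at between-subject r = 0.3/0.5/0.7, and in 5% after M is split. Steps 1 and 2 must also pass. Treating the steps as independent approximates the simulated rates:

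- r = 0.5, total effect 0.6: 0.16 × 0.82 × 0.82 = 0.108 (simulated about 11%)
- r = 0.7, total effect 0.6: 0.29 × 0.82 × 0.82 = 0.195 (about 20%)
- r = 0.5, total effect 0.36: 0.16 × 0.407 × 0.82 = 0.053 (about 5%)
- r = 0.5, total effect 0.24: 0.16 × 0.21 × 0.82 = 0.028 (about 3%)
- r = 0.5, total effect 0: 0.16 × 0.05 × 0.82 = 0.007 (about 0.5%)

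At r = 0.5 and total effect 0.6, the rate is 5–18% for ICC 0.3–0.7. If only stable baseline levels correlate, change scores cancel them and the rate is 2–3%. The interval on the within-subject slope stays at 2–5%.

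**5. Shared session noise.** Section 6.0 (MRI Procedures) places the task and resting-state scans in one exam, and EM performance comes from the same recognition task as the activation contrast. With a residual correlation of 0.1/0.2/0.3 and no true mediation (total effect 0.6, subject-level changes uncorrelated), the plain interval claims falsely in 8/21/43% and the written rule in 7/16/33%.

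**The case against.** The strongest reply is that the gate does useful work. It costs little at the effect the plan assumes, and it holds down false claims when the total effect is small, which is where its power loss is largest. This stands: the two weaknesses appear mostly in different scenarios. It also stands that the plain interval is more exposed to session noise than the rule (item 5), so replacing one yes/no rule with another would be no clear gain.

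Blending also needs subject-level changes that correlate across measures while residuals do not. A shared baseline scan is one route, but the planned baseline covariate would absorb part of it; one check allowing for this gave 7–9% at r = 0.5 and 11–13% at r = 0.7. The 11% and 20% are therefore conditional figures, not expected rates.

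The wording of step 4 leans towards a contrast-level reading, so the ambiguity is confined to steps 1 and 2.

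None of this supplies an interval for the indirect effect, or a reason to prefer a blended slope in a crossover.

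**Conclusion.** The point holds as a moderate, inexpensive improvement to a secondary analysis. The missing interval, the total-effect gate and the undivided mediator are plain in the text. Their size depends on assumed values of a, b, r and ICC; only the 0.6 effect and the 0.5 correlation come from the plan.

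Four stronger readings are tempting and are not supported:

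- *The rule is both underpowered and prone to false claims.* The large power loss needs total effects of 0.24–0.48, while the 11% and 20% need a total effect of 0.6.
- *The stated 0.8 power is wrong.* It reproduces for a treatment difference of 0.6. It simply does not carry over to a four-step rule with a smaller total effect.
- *An interval excluding zero would establish mediation.* Activation and outcome share a scan session, so it would not.
- *The third primary aim is repaired by an interval.* That aim "is to characterize the relationships between EM performance and changes in precuneus functional activation and connectivity". Equation (2) is the only model in section 13.0 linking EM performance to activation, but an interval on a × b does not by itself address the aim.

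The primary contrasts with sham are unaffected.

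**What to change.** In the secondary-analyses paragraph:

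1. In equation (2), replace M with two terms: M minus the subject's mean, and the subject's mean.
2. For 1 Hz–sham and 20 Hz–sham separately, report a × within-subject b with a Monte Carlo or subject-level bootstrap 95% interval as the main mediation result.
3. Report the four steps per contrast as description, not as the deciding rule.
4. Label the result exploratory, state that activation and outcome come from the same scan session, and claim no established mediation from the plain interval alone.
5. Repeat the interval with b moved towards zero by ρ/√(1 − ρ²) × (residual SD of the outcome in (2) / residual SD of M in (3)) for ρ = 0.1, 0.2 and 0.3. Give the largest ρ at which it still excludes zero on the same side.

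The cost is SAP wording and a little code, with no new data. There are two statistical costs. The within-subject slope is less precise when the between-subject slope is also valid (step 3 power 80% against 91% at b = 0.4; 99% against 100% at b = 0.6). The plain interval is also more exposed to session noise, which is why item 5 is needed. If exclusion of zero at ρ = 0.2 were made a requirement, false claims would fall to 1/3/10% at residual r = 0.1/0.2/0.3, but detection would be 27/75/82% at b = 0.4/0.6/0.8. It is better reported than used as a new gate.
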